The End of Treatment and Follow-up visit procedures are listed in Section 8.0 (Protocol Flow Chart) and Section 9.1.9 (Visit Requirements). After the end of treatment, each subject will be followed for 30 days for adverse event monitoring (serious adverse events will be collected for 90 days after the end of treatment as described in Section 9.2.1). Subjects who discontinue for reasons other than progressive disease will have post-treatment follow-up for disease status until disease progression, initiating a non-study cancer treatment, withdrawing consent or becoming lost to follow-up. After documented disease progression each subject will be followed by telephone for overall survival until death, withdrawal of consent, or the end of the study, whichever occurs first.

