X For subjects who have an allogeneic SCT within 24 months of last study treatment, transplant parameters will be collected and specific events will be collected for 18 months from the date of the allogeneic transplant to include graft-versus-host-disease (acute and/or chronic), veno-occlusive disease, febrile syndrome (a steroid-requiring febrile illness without an infectious cause), and encephalitis, for all grades, and regardless of relationship to study drug. Additional medically important adverse events post-allogeneic SCT may be submitted at the Investigator's discretion.

X See table in [section 9.1.7](#) for list of tests to include (not just the comprehensive metabolic panel)

X Thyroid blood tests are only required every other cycle (e.g. day 1 only for odd cycles)

X After 30 day safety visit, only new SAEs considered related to study intervention need to be collected and assessments (as applicable) may be by phone or videoconference. Active AEs at the time of 30 day safety visit should be followed through resolution or stability.

STUDY FLOW CHART – ARM B		Treatment Cycles 												Post-treatment		
Treatment Cycle/Title:		Screening (Visit 1)	1&4				2&5				3&6			Discon	Safety Follow-up	Follow Up Visits
Scheduling Window (Days) ± 2 :			D1	D8	D15	D22	D1	D8	D15	D22	D1	D8	D15			
Informed Consent	X															
Inclusion/Exclusion Criteria	X															
Demographics and Medical History	X															
Prior and Concomitant Medication Review	X		x-----x										x	x		
Post-study anticancer therapy status															x	x 
Review Adverse Events			x-----x										x	x	x 	
Physical Examination	X	x 	x 	x 			x				x			x	x	
Vital Signs and Weight	X		x-----on all days with physical exam or infusion----x										x	x		
ECOG Performance Status	X	x 	x 	x 		x				x			x	x		
Pregnancy Test – Urine or Serum β-HCG	X															
PT/INR and aPTT	X	x 				x				x						
CBC with Differential	X	x 	x	x	x 	x	x	x	x	x	x	x	x	x	x	
Chemistry 	X	x 	x	x		x	x	x	x 	x	x	x	x	x	x	
EBV PCR	x															

STUDY FLOW CHART – ARM B		Treatment Cycles 												Post-treatment		
Treatment Cycle/Title:		Screening (Visit 1)	1&4				2&5				3&6			Discon	Safety Follow-up	Follow Up Visits

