#### 9.1.9.1 Safety Follow-Up Visit

The mandatory Safety Follow-Up Visit should be conducted approximately 30 days after the last dose of trial treatment or before the initiation of a new anti-cancer treatment, whichever comes first. All AEs that occur prior to the Safety Follow-Up Visit should be recorded. Subjects with an AE of Grade  $> 1$  will be followed until the resolution of the AE to Grade 0-1 or until the beginning of a new anti-neoplastic therapy, whichever occurs first. SAEs that occur within 90 days of the end of treatment or before initiation of a new anti-cancer treatment should also be followed and recorded.

For subjects who have an allogeneic SCT within 24 months of last study treatment, transplant parameters will be collected and specific events will be collected for 18 months from the date of the allogeneic transplant to include graft-versus-host-disease (acute and/or chronic), veno-occlusive disease, febrile syndrome (a steroid-requiring febrile illness without an infectious cause), and encephalitis, for all grades, and regardless of relationship to study drug. Additional medically important adverse events post-allogeneic SCT may be submitted at the Investigator's discretion. If available and relevant to an event post-allogeneic SCT, concomitant medications and/or laboratory results may also be reported.

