### **9.2.1 Time Period and Frequency for Collecting AE, SAE, and Other Reportable Safety Event Information**

All AEs, SAEs, and other reportable safety events that occur after the consent form is signed but before intervention allocation/randomization must be reported by the investigator if the participant is receiving placebo run-in or other run-in treatment, if the event cause the participant to be excluded from the study, or is the result of a protocol-specified intervention, including but not limited to washout or discontinuation of usual therapy, diet, or a procedure.

- All AEs from the time of intervention allocation/randomization through 30 days following cessation of study intervention must be reported by the investigator.
- All AEs meeting serious criteria, from the time of intervention allocation/randomization through 90 days following cessation of study intervention or 30 days following cessation of study intervention if the participant initiates new anticancer therapy, whichever is earlier, must be reported by the investigator.
- All pregnancies and exposure during breastfeeding, from the time of intervention allocation/randomization through 120 days following cessation of study intervention, or 30 days following cessation of study intervention if the participant initiates new anticancer therapy must be reported by the investigator.
- Additionally, any SAE brought to the attention of an investigator at any time outside of the time period specified above must be reported immediately to Merck if the event is considered drug-related.

Investigators are not obligated to actively seek AEs or SAEs or other reportable safety events in former study participants. However, if the investigator learns of any SAE, including a death, at any time after a participant has been discharged from the study, and he/she considers the event to be reasonably related to the study intervention or study participation, the investigator must promptly notify Merck and the Sponsor/UVA CC/GTcLC.

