### 9.2.1.3 Serious Adverse Event Reporting to Sponsor/UVA CC/GTcLC /DSMC/IRB

The study clinician will report to the sponsor (see Study Reference Manual for contact information and instructions) any serious adverse event, whether or not considered study intervention related, including those listed in the protocol, package insert or investigator brochure and must include an assessment of whether there is a reasonable possibility that the study intervention caused the event.

All serious adverse events (SAEs) will be followed until satisfactory resolution or until the site investigator deems the event to be chronic or the participant is stable. Other supporting documentation of the event may be requested by the UVA Coordinating Center (UVA CC/GTcLC /Sponsor) and should be provided as soon as possible.

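### Flow-chart footnotes limit SAE collection after the 30-day visit to related events, while Sections 9.2.1, 7.10 and 9.1.9.1 require all SAEs to day 90

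*Protocol*

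**What the plan says.** Section 8.0 attaches the same footnote to the adverse-event review at the post-treatment follow-up visits in all three arms (footnote 15 in Arm A, footnote 17 in Arms B and C): "After 30 day safety visit, only new SAEs considered related to study intervention need to be collected". These visits are scheduled every 8 weeks after discontinuation.

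Four other places in the protocol apply no causality filter:

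- Section 9.2.1 covers "All AEs meeting serious criteria, from the time of intervention allocation/randomization" and runs "through 90 days following cessation of study intervention or 30 days following cessation of study intervention if the participant initiates new anticancer therapy", whichever comes earlier. It limits reporting to drug-related SAEs only outside that period.
- Section 7.10 says that "serious adverse events will be collected for 90 days after the end of treatment as described in Section 9.2.1".
- Section 9.1.9.1 says that "SAEs that occur within 90 days of the end of treatment or before initiation of a new anti-cancer treatment should also be followed and recorded".
- Section 9.2.1.3 requires reports to the sponsor of "any serious adverse event, whether or not considered study intervention related".

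For adverse events in general, 9.2.1 sets a shorter period, "through 30 days following cessation of study intervention must be reported by the investigator". The 90-day question therefore concerns SAEs only.

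**The concern.** The footnotes bring in a related-only restriction as soon as the 30-day visit is over. Section 9.2.1 brings it in only after its own window closes, which is day 90 for a participant on no new therapy. A site that works from the flow chart at a follow-up visit would leave out unrelated SAEs that 9.2.1 makes reportable.

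Safety and toxicity is a primary objective (Section 3.1), and Section 10.6 tabulates the frequency, proportion and severity of adverse events by dose level and by arm. The trial is open-label (Section 7.5) and the investigator judges causality (Section 9.2). Under the footnotes, whether a late SAE enters the database at all would depend on that judgement. At stake is the completeness of all-cause SAE counts in the later part of follow-up, in a trial of at most 38 participants where a few events would show in an arm-level table.

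A second discrepancy concerns the point at which SAE recording stops when new anticancer therapy begins. Sections 9.1.9.1 and 9.2.1 set that point differently.

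**Working it through.** No sample size or error rate is involved. The check sets the rules side by side and counts days.

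**Rule for an SAE judged unrelated, no new anticancer therapy started**

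| Source | Up to the 30-day visit | From then to day 90 | After day 90 |
|---|---|---|---|
| 8.0, footnotes 15/17/17 | collected | not required | not required |
| 9.2.1 | required | required | not required |
| 7.10 | collected | collected | not covered |
| 9.1.9.1 | recorded | recorded | not covered |

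An SAE judged related is collected in days 31 to 90 under every one of these rules. The conflict is confined to SAEs judged unrelated.

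**Length of the conflict.** The inputs are the 90-day window (9.2.1, 7.10, 9.1.9.1) and the 30-day visit (8.0).

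- Days in conflict: 90 − 30 = 60.
- Share of the window: 60/90 = 66.7%.
- If the flow chart's ±2-day window is applied to the 30-day visit: (90 − 32)/90 = 64.4% to (90 − 28)/90 = 68.9%.

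**Visits affected.** Taking discontinuation and last dose as the same day, 8-weekly follow-up falls at about days 56 and 112. Only day 56 lies within days 31 to 90, so one scheduled visit per participant falls in the disputed period.

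**Participants who start new anticancer therapy.** Read literally, 9.2.1 then ends its all-SAE window at day 30, and its conflict with the footnotes over days 31 to 90 disappears. On the reading that 9.1.9.1 records all SAEs until the new therapy starts, some conflict with the footnotes remains. For assumed start days t, the share is (t − 30)/t:

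- t = 45: 15/45 = 33%
- t = 60: 30/60 = 50%
- t = 75: 45/75 = 60%

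**New-therapy cut-offs compared**

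| New therapy starts | 9.1.9.1 (recording until new therapy) | 9.2.1 (30 days after cessation) | Difference |
|---|---|---|---|
| Day 10 | to day 10 | to day 30 | 9.2.1 longer by 20 days |
| Day 60 | to day 60 | to day 30 | 9.1.9.1 longer by 30 days |

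The sign changes at day 30, so neither section is always the more complete.

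**Dose-finding.** Under Section 5.3 only DLTs before cycle 2 enter escalation decisions, and a DLT must be judged at least possibly related. A rule that drops unrelated SAEs late after treatment does not alter DLT counts, model-based allocation or the MTD.

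**The case against.** The strongest reply is that the protocol has already made its choice. Section 9.2.1 says these SAEs must be reported, 7.10 names 9.2.1 as its source, and 9.1.6.1 sends readers to Section 9.2 for recording adverse events. The footnote says only what needs to be collected and forbids nothing. On this view it is a drafting slip that sites would read through.

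Part of this stands. The problem is an internal inconsistency and not a deliberate design choice, and the footnotes are the outlier. But 9.1 presents the flow chart as the summary of what is done at each visit, and 9.1.6.1 also ties adverse-event assessment to it. No clause gives 9.2.1 precedence, so a site could follow the footnote in good faith. Whether any site has done so is not known from the document.

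A reader might draw stronger conclusions that the protocol does not support:

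- **That two-thirds of the window is affected for everyone.** It is a maximum, for participants who start no new therapy. The day-56 visit is not universal either: after progression, 7.10 moves participants to telephone follow-up for survival. The protocol gives no rate of new therapy.
- **That late immune-related SAEs would be lost.** Section 7.3.1 does warn of events months after the last dose, but SAEs judged related are collected under both rules, and 11.5.4 generally favours attribution to the whole regimen.
- **That counts from different sites cannot be pooled.** Related-SAE counts can be. Only all-cause counts after the 30-day visit might differ, and only if sites follow different rules.
- **That open-label causality biases a comparison.** There is no control arm, and the change log notes that the arms are not being compared.
- **That Table 16 independently fixes 90 days.** It asks for all SAEs through the protocol-specified follow-up period without giving a length, and it concerns reporting to the drug supplier.

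**Conclusion.** The inconsistency is real, is in current text and appears in all three arms. For participants who start no new anticancer therapy, up to 60 of 90 post-treatment days (67%) fall under conflicting rules, including the follow-up visit at about day 56. The consequence is limited to SAEs judged unrelated: all-cause late SAE counts could be too low or could vary by site. The number of events at risk cannot be estimated from the document.

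The new-therapy cut-offs in 9.1.9.1 and 9.2.1 also disagree, by 20 days one way or 30 days the other in the two examples. This rests on reading 9.1.9.1 as ending recording when new therapy starts. Its sentence does not say which limit applies first, so that is one reading and itself needs clarifying.

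The point deserves correction because safety is a primary objective and the edit is small. It does not call the dose-finding design into question.

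**What to change.** 1. Amend footnote 15 (Arm A) and footnote 17 (Arms B and C) so that all SAEs, whatever their judged causality, are collected through the window in 9.2.1, and only related SAEs after that window closes.
2. Reconcile 9.1.9.1 and 9.2.1 on new anticancer therapy with one rule that does not shorten all-cause SAE collection before the new therapy begins. Copying the present 9.2.1 cut-off into 9.1.9.1 would not do: read literally, it would remove 30 days of collection for a participant whose new therapy starts on day 60. State explicitly which limit applies when therapy starts before day 30 and which when it starts later, and make the footnotes refer to the reconciled rule.

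The cost is three footnote edits and a sentence in each of two sections. For participants on no new therapy, any extra SAE forms for days 31 to 90 are already required by 9.2.1. The added burden from the second change depends on the rule chosen. Sites should be told of the change, and participants already past their 30-day visit but still within 90 days should be checked for unrecorded SAEs.

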## **5.3 Dose Limiting Toxicities**

A dose limiting toxicity (DLT) is defined as any toxicity that occurs that is considered at least “possibly related to the study drug administration”. Only DLT’s that occur prior to initiation of cycle 2 will be used to determine dose escalation/de-escalation decisions.

DLT criteria are defined as follows:

1. Any non-hematologic toxicity greater and/or equal to grade 3, except for:
  - Alopecia
  - Untreated nausea or vomiting;
  - Untreated constipation or diarrhea;
  - Untreated dehydration or fatigue uncontrolled;
  - Any liver function test including AST/ALT, GGT, Alkaline phosphatase elevation that has returned to grade 1 or baseline by day1 of cycle 2;
2. Grade 4 neutropenia lasting more than 5 days despite GCS-F support;
3. Febrile neutropenia (ANC <  $1000/\text{mm}^3$  with a single temperature of  $> 38.3^\circ\text{C}$  or sustained temperature of  $\geq 38^\circ\text{C}$  for over one hour);
4. Any grade 4 thrombocytopenia or grade 3 thrombocytopenia with clinically significant bleeding or any grade-3 thrombocytopenia requiring platelet transfusion
5. Grade 4 anemia unexplained by underlying disease involvement;

6. Failure to meet the required blood parameters for cycle 2 day 1.

Management and dose modifications associated with adverse events will be described in the following sections 7.0, 7.1, 7.2 (Dose selection, dose delays, dose modification).

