## 8.0 TRIAL FLOW CHART

STUDY FLOW CHART – ARM A	Treatment Cycle/Title: Screening (Visit 1)	Treatment Cycles 										Post-treatment		
		1&4				2&5			3&6			Discon	Safety Follow-up	Follow Up Visits
		D1	D8	D15	D22	D1	D8	D15	D1	D8	D15			
Scheduling Window (Days) ± 2 :												At time of Discon	30 days post discon	Every 8 weeks post discon
Informed Consent	x													
Inclusion/Exclusion Criteria	x													
Demographics and Medical History	x													
Prior and Concomitant Medication Review	x	x-----x								x	x			
Post-study anticancer therapy status													x	x 
Review Adverse Events		x-----x								x	x		x 	
Physical Examination	x	x 	x 	x 	x 	x			x			x	x	
Vital Signs and Weight	x	x-----on all days with physical exam or infusion-----x								x	x			
ECOG Performance Status	X	x 	x 	x 	x 	x 			x			x	x	
Pregnancy Test – Urine or Serum β-HCG	X													
PT/INR and aPTT	X	x 				x			x					
CBC with Differential	x	x 	x	x	x	x	x	x	x	x	x	x	x	

STUDY FLOW CHART – ARM A	Treatment Cycle/Title: Screening (Visit 1)	Treatment Cycles 									Post-treatment			
		1&4			2&5			3&6			Discon	Safety Follow-up	Follow Up Visits	
		D1	D8	D15	D22	D1	D8	D15	D1	D8	D15			
Scheduling Window (Days) ± 2 :												At time of Discon	30 days post discon	Every 8 weeks post discon
Chemistry 	x	x 	x	x	X	x	x	x	x	x	x	x	x	
EBV PCR	x													
Urinalysis	x													
T3, FT4 and TSH	x	x 				x 			x 			x	x	
Tumor Imaging 	x 					x 			x 					
mSWAT and photograph of skin involvement 	x 	x 				x 			x 					
Archival/Newly Obtained Tissue Collection	x 								x 					
Correlative Studies Blood Collection		x	x 	x 		x			x			x		
Pharmacokinetics (PKs) 		x	x 	x 										
Pralatrexate IV push		x	x	x		x	x	x	x	x	x			
Pembrolizumab Infusion		x 			X			x		x				

X After cycle 6, cycle 7 will follow the calendar for cycle 1&4, cycle 8 will follow the calendar for cycle 2&5, cycle 9 will follow the calendar for cycle 3&6 etcetera

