X Cycle 1 only. Additional pharmacokinetics sample (only for patients at UVA) will be obtained at day 5 to determine drug steady state.

X Decitabine will be given from day 1 to day 5 (or day 3, depending on dose level) of each cycle as described in section 5.2.3

X Pembrolizumab will be administered every 3 weeks (Q3W). In Arm B, pembrolizumab administration will be started on day 8 of cycle 1 as described in section 5.2.1.

X For cycle 1 day 1, laboratory screening tests can be considered valid for treatment on cycle 1 day 1 as long as they are performed within the screening laboratory test window (10 days). After Cycle 1, pre-dose laboratory procedures can be conducted up to 72 hours prior to dosing.

X Pharmacokinetics (PKs) and correlative study blood draws at Days 8 and 15 in a cycle are only for Cycle 1 (not cycles 4, 7, etc.)

X For subjects who have an allogeneic SCT within 24 months of last study treatment, transplant parameters will be collected and specific events will be collected for 18 months from the date of the allogeneic transplant to include graft-versus-host-disease (acute and/or chronic), veno-occlusive disease, febrile syndrome (a steroid-requiring febrile illness without an infectious cause), and encephalitis, for all grades, and regardless of relationship to study drug. Additional medically important adverse events post-allogeneic SCT may be submitted at the Investigator's discretion.

X Thyroid blood tests are only required every other cycle (e.g. day 1 only for odd cycles)

X After cycle 2, the day 22 CBC with differential is not required (e.g. not for cycles 5, 8, etc.)

X After 30 day safety visit, only new SAEs considered related to study intervention need to be collected and assessments (as applicable) may be by phone or videoconference. Active AEs at the time of 30 day safety visit should be followed through resolution or stability.

X See table in [section 9.1.7](#) for list of tests to include (not just the comprehensive metabolic panel)

X CBC with differential at Day 22 is for cycle 1 only (e.g. not for cycles 4, 7, etc)

STUDY FLOW CHART – ARM C	Treatment Cycle/Title:	Treatment Cycles 								Post-treatment			
		Screening (Visit 1)	1&4				2&5		3 &6		Discon	Safety Follow-up	Follow Up Visits
			D1	D8	D15	D22	D1	D22	D1	D15			

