Scheduling Window (Days) ± 2 :											At time of discon	30 days post discon	Every 8 weeks post discon
Informed Consent	x												
Inclusion/Exclusion Criteria	x												
Demographics and Medical History	x												
Prior and Concomitant Medication Review	x		x-----x							x		x	x
Post-study anticancer therapy status											x		x 
Review Adverse Events			x-----x							x		x	x 
Physical Examination	x	x 	x 				x		x		x	x	
Vital Signs and Weight	x		x-on all days with physical exam or infusion-x							x		x	
ECOG Performance Status	x	x 	x				x		x		x	x	
Pregnancy Test – Urine or Serum β-HCG	x												
PT/INR and aPTT	x	x 					x		x				
CBC with Differential	x	x 	x	X 	x 		x	x 	x	x	x	x	
Chemistry 	x	x 	x	X 			x	x	x	x	x	x	
EBV PCR	x												

STUDY FLOW CHART – ARM C		Treatment Cycles 								Post-treatment		
		Screening (Visit 1)	1&4			2&5		3 &6		Discon	Safety Follow-up	Follow Up Visits
Scheduling Window (Days) ± 2 :			D1	D8	D15	D22	D1	D22	D1	D15	At time of discon	30 days post discon
Urinalysis	x											
T3, FT4 and TSH	x	x 					x 		x 		x	x
Tumor Imaging 	x 						x 		x 			
mSWAT and Photograph of skin involvement 	x 	x 					x 		x 			
Archival/Newly Obtained Tissue Collection	x 								x 			
Correlative Studies Blood Collection		x	x 	x 		x		x		x		
Pharmacokinetics (PKs) 		x 										
Decitabine		x 					x 		x 			
Pembrolizumab			x 				x 	x 		x 		

X After cycle 6, cycle 7 will follow the calendar for cycle 1&4, cycle 8 will follow the calendar for cycle 2&5, cycle 9 will follow the calendar for cycle 3&6 etcetera

X Physical exam should be performed ONLY at D1 of each cycle beyond cycle 4

X ECOG should be only performed at D1 of each cycle beyond cycle 4

X CT/PET or CT will be performed at screening within 4 weeks from treatment start date and after cycle 2; then it will be repeated every 3 to 4 cycles at the discretion of the treating physician.

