X mSWAT and standardized photographs of skin involvement are strongly recommended at screening or cycle 1 day 1 not at both timepoints. mSWAT is required to be performed after cycle 2 and then it will be repeated every 3 to 4 cycles at the discretion of the treating physician. mSWAT will be performed along with CT/PET or CT evaluation.

X Blood samples and tissue collection should be obtained in the screening phase of the study.

X Tissue collection of the tumor lesion (including possible FNA or ultrasound when indicated per standard care) should be obtained, if possible, at screening or within Cycle 1 (please refer to section [6.1.1: Subject Inclusion Criteria](#) number 7). An optional biopsy may be performed post Cycle 3 or 4.

X The pharmacokinetics (PKs) blood draw are only for patients at UVA. See [section 9.1.7.3](#) for details. X Cycle 1 only. Additional pharmacokinetics sample (only for patients at UVA) will be obtained on the final day (in Cycle 1) of scheduled treatment for the participant to determine drug steady state. See [section 9.1.7.3](#) for details.

X Decitabine will be given from day 1 to day 5 (or day 3, depending on dose level) of each cycle as described in section 5.2.3

X Pembrolizumab will be administered every 3 weeks (Q3W). In Arm C, pembrolizumab administration will be started on day 8 of cycle 1 as described in section 5.2.1.

X For cycle 1 day 1, laboratory screening tests can be considered valid for treatment on cycle 1 day 1 as long as they are performed within the screening laboratory test window (10 days). After Cycle 1, pre-dose laboratory procedures can be conducted up to 72 hours prior to dosing.

X Correlative study blood draws at Days 8 and 15 in a cycle are only for Cycle 1 (not cycles 4, 7, etc.). Labs (CBC with differential and Chemistry) on day 15 are for cycle 1 only.

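### Cycle 1 of Arms B and C schedules no chemistry between day 15 and cycle 2 day 1, so a short, silent, non-liver chemistry DLT late in the cycle can go unseen

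*Protocol*

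**What the plan says.** Protocol Section 5.3 defines the outcome that drives dose finding. Criterion 1 is "Any non-hematologic toxicity greater and/or equal to grade 3", with listed exceptions. One exception is a liver-test "elevation that has returned to grade 1 or baseline by day1 of cycle 2". On timing, "Only DLT’s that occur prior to initiation of cycle 2 will be used to determine dose escalation/de-escalation decisions". Criterion 6 adds failure to meet the blood parameters for cycle 2 day 1; among chemistry tests, Section 5.4 lists creatinine, AST/ALT and bilirubin.

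The cycle 1 chemistry rows in Section 8.0 differ by arm (footnote numbers run into the marks):

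- Arm A: "Chemistry 13 x x 10 x x X x". The marks are screening, days 1, 8, 15 and 22, then cycle 2 day 1.
- Arm B: "Chemistry 18 X x 12 x x x". The marks are screening, days 1, 8 and 15, then cycle 2 day 1. The day 22 cell is blank.
- Arm C: "Chemistry 18 x x 12 x X 13". The marks are screening, days 1, 8 and 15, with day 22 again blank. Footnote 13 says "Labs (CBC with differential and Chemistry) on day 15 are for cycle 1 only".

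Both the Arm B and Arm C charts mark a count on day 22, with footnote 19: "CBC with differential at Day 22 is for cycle 1 only (e.g. not for cycles 4, 7, etc". That footnote concerns the blood count and is not itself wrong. The gap is the empty chemistry cell beside it.

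**The concern.** Creatinine, glucose and electrolytes are all in the Table 15 chemistry panel. A grade 3 or higher abnormality in any of them is a DLT if at least possibly related to study drug, and only the liver tests have a recovery exemption. These events may cause no symptoms, so they are found mainly when blood is drawn.

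The unobserved stretch is not a quiet one. Section 5.2.1 starts pembrolizumab on day 8 in Arms B and C, so days 15 to 29 are the second and third weeks after its first dose. Every Arm B combination in Section 10.1 also gives pralatrexate on day 15, so in Arm B these are the two weeks after the last pralatrexate dose of the cycle. Unlike Arm A, the two charts mark no physical examination on cycle 1 day 22, which removes one prompt for an unscheduled test.

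Section 10.1 uses cohorts of one and refits the model after each participant, so a single missed DLT enters the next dose decision as a non-DLT.

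**Working it through.** The protocol gives no detection figure, so there is none to reproduce. It also gives no onset times or durations for chemistry events; those below are assumptions, shown over a range.

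**1. Scheduled post-baseline chemistry in the DLT window.** The cycle 2 day 1 draw is taken before dosing, so it lies inside the window; call it day 29.

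- Arm A: days 8, 15, 22, 29, which is 4 draws.
- Arms B and C: days 8, 15, 29, which is 3 draws.
- Longest interval in Arms B and C: 29 − 15 = 14 days, against 7 in Arm A. Section 9.1.7 allows pre-dose tests up to 72 hours early, which makes it 26 − 15 = 11 days.

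**2. Detection under uniform onset.** An event lasting L days is seen if a draw falls between its onset and its end. With onset uniform over days 1 to 29 (28 days):

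- L ≤ 7: Arm A detects 4L/28 and Arms B and C detect 3L/28, a ratio of 3/4 = 0.75. At L = 5 this is 0.714 against 0.536.
- 7 < L ≤ 14: Arm A detects all, and Arms B and C detect (7 + 7 + L)/28. At L = 10, 24/28 = 0.86; at L = 12, 26/28 = 0.93; at L = 14, 28/28 = 1.00.

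**3. Sensitivity of the ratio (Arms B and C to Arm A).**

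| Assumed onset | L ≤ 7 | L = 10 | L ≥ 14 |
|---|---|---|---|
| Uniform, days 1–29 | 0.75 | 0.86 | 1.00 |
| Uniform, days 8–29 | 0.67 | 0.81 | 1.00 |
| Uniform, days 15–29 | 0.50 | 0.71 | 1.00 |

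With exponential durations of mean 3 to 14 days and onset over days 1 to 29, the ratio runs from 0.78 to 0.90. With the cycle 2 draw taken on day 26 and onset over days 1 to 29, it is 0.75 up to 4 days, 0.84 at 7 days, 0.96 at 10 days and 1.00 from 11 days.

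**4. What the DLT rules leave exposed.**

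- A creatinine, AST/ALT or bilirubin value still outside the Section 5.4 limits at the cycle 2 day 1 draw is a DLT under criterion 6.
- A grade 3 or higher electrolyte or glucose value still present at that draw meets criterion 1 directly, if at least possibly related.
- A listed liver-test rise that has recovered by then is exempt, so seeing it on day 22 would add no DLT.
- What remains is a non-liver abnormality of grade 3 or higher, without symptoms, that starts after day 15 and resolves before the cycle 2 day 1 draw.

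**5. Effect of one missed DLT in Arm B.** Section 10.1 reports 1 DLT in 4 participants, all on Combination 8, and assigns the next participant there. With all data on one combination, the one-parameter model's fitted rate there equals the observed rate.

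- DLT seen: 2/5 = 0.40. DLT missed: 1/5 = 0.20.
- At 0.40 the power is ln 0.40 / ln 0.25 = 0.661. The skeleton values that Combinations 5 and 6 take across the five orderings become 0.174^0.661 = 0.315, 0.11^0.661 = 0.232 and 0.062^0.661 = 0.159. All are nearer 0.25 than 0.40 is.
- At 0.20 every other combination is fitted lower still, so Combination 8 remains closest to 0.25.

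**6. After the change.** A day 22 chemistry draw gives Arms B and C the same four draws as Arm A, and the ratio becomes 1.00 under every assumption above.

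**The case against.** A reader might infer that chemistry-based DLTs are about half as likely to be seen in Arms B and C as in Arm A. The documents do not support that. One half applies only to events of 7 days or less that start after day 15. Over the whole DLT window the count is 3 draws against 4, and the rules in step 4 close the gap for lasting and for liver abnormalities.

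A reader might also infer that a seen chemistry DLT would send the next Arm B participant one combination down. Section 10.2 does not say so. Its rules after a DLT cover mucositis, thrombocytopenia and neutropenia, and state nothing for a creatinine, glucose or electrolyte DLT. Nor is the closest fitted value to 25% necessarily the next one in the ordering: 0.232 is nearer than 0.315. Only the change in the fitted rate can be claimed.

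The difference between arms has a plausible explanation. Day 22 of cycle 1 is a pembrolizumab day in Arm A but not in Arms B and C, although the protocol does not give this as the reason. Each arm has its own model and MTD, and the Section 12.0 log notes that arms are not being compared, so bias in a between-arm comparison is not the issue. Adverse events are reviewed throughout treatment, and Section 9.1 allows unscheduled tests.

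All of this stands and narrows the point. It does not remove the blind spot for silent events, which ongoing review and symptom-led testing are least likely to catch. The protocol's own log points the same way: the day 22 count was added to Arms B and C on safety grounds, and when laboratory tests were cut from days without dosing or examination, cycle 1 was excepted.

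**Conclusion.** The point holds in a limited form. Arms B and C have one fewer scheduled chemistry draw than Arm A inside the DLT window, and the missing draw leaves the last two weeks of cycle 1 uncovered. The exposed events are short, silent, non-liver abnormalities of grade 3 or higher. Relative detection under uniform onset over days 1 to 29 is 0.75 at worst and reaches 1.00 at 14 days. These ratios rest on assumed onset and duration, on draws taken on their nominal days except in the day 26 check, and on no unscheduled testing. How often such events occur cannot be judged from the protocol.

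The consequence is a possible undercount in a model refitted after every participant; in Arm B one event separates a fitted 0.40 from 0.20 at Combination 8. This is an inexpensive improvement to DLT ascertainment, not a flaw that undermines the design.

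**What to change.** In the Arm B chart of Section 8.0, mark chemistry (the Table 15 panel) on cycle 1 day 22, with a footnote limiting it to cycle 1 as is done for the count. Make the same change in the Arm C chart for any participants still to be enrolled. Section 10.4 still lists additional Arm C participants, but Section 7.6 opens Arm B only after Arms A and C have completed enrollment and Arm B already has 4 participants, so the practical gain is probably mainly in Arm B.

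The cost is one more tube at a draw that already takes place and a small laboratory charge, with no added visit. The DLT definition, the model and the stopping rules need no change for this.
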